Originally, an intention-to-treat analysis (ITT) was planned as the primary analysis. Nevertheless, during the study it was observed that after allocation, several patients immediately refused CLI treatment and either chose to be treated with DBS or quitted study participation. Analyzing these patients in an ITT could have introduced a significant bias, as their apparent preference for DBS made them not representative of a population that considered CLI a suitable treatment for advanced PD. Furthermore, for the patients for whom post-baseline data were not available, all these data would have had to be imputed, contributing to the risk of bias. A modified intention-to-treat (mITT) population was introduced as the primary analysis, because analysis in the ITT population including all randomized individuals was considered less valid.⁷ The mITT population included all randomized patients who received the allocated treatment and continued in the RCT after randomization. Additionally, in line with the proposed strategy for ITT analyses for trials with incomplete outcome data as proposed by White et al.,⁷ sensitivity analyses were performed to explore the robustness of the main analyses in the mITT population and included analyses in all randomized patients (the ITT population). Please see “Sensitivity analysis” for details on page 12.

While conducting the study, it was observed that comorbidities had a negative impact on completeness of the follow-up data. To assess for a possible bias towards a selective data collection of healthier patients, treating physicians of patients that had dropped out of the study were contacted to obtain additional information on the general health status and level of functioning of these patients. Please see also “Patient replacement and missing data” on page 10.

Study methods

Outcomes - randomized controlled trial

Primary outcomes

The main clinical outcome was the change from baseline to 12 months after initiation of treatment in PDQ-39 (score 0-100).⁸

The primary health economic outcomes are elaborated on page 19.

Secondary outcomes

- PD motor symptoms -- Movement Disorder Society’s Unified Parkinson’s Disease Rating Scale (MDS-UPDRS) part III in on-drug state (score range 0-132) ²;
- Motor experiences of daily living-- MDS-UPDRS part II in on-drug phase (score range 0-52) ²;
- Dyskinesia -- Clinical Dyskinesia Rating Scale (CDRS, score range 0-28) in on-drug state ⁹;

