II - In case both follow-up PDQ-39's were missing (*i.e.*, nine and 12 months) but a baseline PDQ-39 was available, multiple imputation was used by fully conditional specification using predictive mean matching with five data sets and with potentially relevant variables at baseline (*e.g.*, age, sex, PDQ-39), previously observed outcomes and adverse events as predictors. The predictive mean matching imputation was performed separately per treatment group of the mITT population and chosen to ensure that imputed values were in the appropriate range.¹⁸ Additionally, we repeated this imputation of the PDQ-39 for the total mITT population as a scenario analysis.

III - For patients with a missing baseline PDQ-39, the imputation method as described in II was used, with follow-up PDQ-39 score(s) as covariate(s).

Since missing values were expected to be missing not at random, a conformity scenario and multiple worst-case scenarios for the mITT analysis were predefined, making use of additionally gathered data if possible. If lost to follow-up, the patients' treating physicians were asked to provide information on these patients regarding their treatment and functioning at 12 months after start of the allocated treatment (*i.e.*, deceased and if so, cause of death; use of the allocated treatment; use of the alternative than allocated treatment; living at home or in a health care facility; and modified Rankin scale).¹⁹ Loss to follow-up because of clinical improvement was deemed unlikely, therefore the conformity scenario for a patient with a missing 12-month PDQ-39 summary index score was to assign the mean PDQ-39 value in the allocated treatment arm. Possible worst-case scenarios were: (A) to assign the lowest assessed PDQ-39 in both treatment arms, and (B) scenario 1 minus ½ minimal clinically important difference (*i.e.*, ½ of -1,6 as defined in literature).²⁰ Based on the additional data acquired in case of loss to follow-up, the most applicable worst-case scenario was selected and justified.

In case of death, the 9-month follow-up PDQ-39 was carried forward if available. For patients alive at the moment of the 9-month follow-up, but without available PDQ-39 at that moment, the 9-month imputed PDQ-39 was carried forward. In case of death before the 9-month follow-up time point, no PDQ-39 summary index scores were used for this patient.

Secondary outcomes

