In line with the proposed strategy for ITT analyses for trials with incomplete outcome data as proposed by White et al, analyses were performed in the ITT population, including the patients who had been excluded from the mITT population (*i.e.*, patients who immediately after randomization either had chosen not to accept the allocated treatment or had quitted participation in the study).⁷ For missing values for the main clinical outcome in the analyses in the ITT population, the approach for handling missing values as used for the mITT analyses as described in “Patient replacement and missing data” on page 10 was applied; first making use of the previously imputed values for the mITT population and additionally imputing missing values of the ITT-population based on the total population according to the conformity scenario and the most applicable worst case scenario chosen for the mITT analysis. In addition, a “best case” scenario was applied as for patients who immediately quitted study participation after randomization and for whom the main clinical outcome at 12 months was missing, a favorable outcome was possible. In this scenario, for patients who immediately quitted study participation after randomization, missing values for the 12-month PDQ-39 summary index score were imputed with the highest PDQ-39 in the treatment arm the patient had been allocated to. Other missing values were imputed according to the previously described conformity scenario.

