The primary health outcome in the cost-effectiveness analysis was the change in the PDQ-39 between baseline and 12 months after randomization. The change score showed the increase or decrease in number of difficulties across eight different dimensions of health (including mobility, activities of daily living, emotional well-being, and stigma) as experienced by patients in the preceding month. Dimension scores are coded on a scale of 0 (perfect health as assessed by the measure) to 100 (worst health as assessed by the measure). The change score was defined as the mean score on the eight scales at month 12 minus the mean score at baseline, in theory ranging from -100 to +100 with a score of 0 representing 'no change'.

The primary health outcome in the cost-utility analysis was the number of QALYs. Patient's health status was assessed with the EQ-5D-3L at baseline, one week, three months, six months, nine months, and 12 months post randomization. The EQ-5D contained five items: mobility, self-care, usual activities, pain/complaints, and mood (anxiety/depression).³¹ Each item had three response options: no problems, some problems, or serious problems. EQ-5D scoring profiles at successive measurements were converted into health utility scores using general population based tariffs of time trade-off ratings of health states.³² QALYs were calculated by taking the product sum of the health utility scores during follow-up and the interval lengths in years in-between successive measurements.

Health economic analysis methods

Analysis population

The CEA and CUA were done with the modified intention-to-treat population (see page 9) with references to the CONSORT-flow diagram in Figure SAP-1 and the baseline characteristics of the two RCT-subpopulations in Table EE1. Summary statistics for health utility scores at baseline were included in the manuscript text.

Cost-effectiveness threshold

The applied cost-effectiveness threshold for the sample size calculation was €120,000 as described and substantiated in the published study protocol.¹

Statistical decision rules

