For missing health utility data over time among patients alive and for missing data on resource use during follow-up the choice of imputation approach depended on the observed missing data pattern and whether or not missingness was associated with baseline variables or previously observed outcomes. Missingness of data (completely) at random was handled with multiple imputation as described above (see page 10).

In a sensitivity analysis potential missingness of data not at random was addressed to account for the expectation by the treating clinicians that missingness of data may well depend on a worsened health status (see also page 10). The following scenarios were addressed in this sensitivity analysis by shifting the costs and health outcomes from the missingness (completely) at random imputation:

- a) increasing actually imputed costs by 20% and 40%
- b) increasing actually imputed PDQ-39 summary index scores changes by 20% and 40%
- c) decreasing actually imputed QALYs by 20% and 40%
- d) combining a) and b)

e) combining a) and c).

Findings of the clinical analyses might have suggested to explore additional scenarios for the sensitivity of the economical evaluation. The higher its impact, the more extensively the sensitivity analysis was reported in the main text, with the remainder reported in the Supplementary Material.

The handling of missing data applied recommendations by Faria et al.³⁴

Cost-effectiveness

Incremental analysis

Differences in costs and differences in changes in PDQ-39 from baseline between the treatment groups were used to calculate the incremental cost-effectiveness ratio (ICER), again following non-parametric bootstrapping drawing 2,500 samples of the same sizes as the original samples and with replacement to account for sampling variability. Likewise, differences in costs and differences in QALYs were used to calculate the incremental cost-utility ratio (ICUR). Differences in costs and the associated differences in health outcomes were plotted with cost-effectiveness planes,³⁵ for example see Figure EE-1.

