For each of the 2,500 bootstraps the net health benefits (NHB) of CLI versus DBS were calculated based on the ICERs for different levels of willingness-to-pay up to €3,000 per additional unit decrease in change in PDQ-39 (NHB_{PDQ-39}), respectively based on the ICURs for willingness-to-pay levels up to €160,000. Cost-effectiveness acceptability curves were plotted to represent uncertainty,³⁶ showing the probability of CLI being cost-effective in comparison with DBS at each level of willingness to pay, see Figure EE-2.

Subgroup analyses

Considering the limited patient numbers, potentially uneven distributions of baseline characteristics despite randomization were exploratory addressed by subgroup analyses for hypothesis generation. Also, a preplanned subgroup analysis by median age was performed to detect a potential influence of being more vulnerable at a higher age.

Additional sensitivity analyses

Apart from addressing the uncertainty of missing data structures, additional sensitivity analyses were performed for the lengths of the life cycles of the DBS and CLI equipment and corresponding depreciation period (6 to 8 years in steps of 1 year versus 5 years).

Scenario analyses

A scenario analysis for the ICUR was performed to correct for health utility scores at baseline by subtracting for each patient the baseline score from the calculated QALYs during the follow-up of 12 months. Another scenario analysis was done to report the ICUR from an international perspective by applying the time trade-off based on valuation of health states based on preferences from the UK general population to the EQ-5D-3L health status profiles and conversion of Euros into English Pound by applying purchasing power parities from the Organisation of Economic Cooperation and Development (or 0.688 divided by 0.772 in 2020).^{37,38}

Table EE2a. Mean per patient use of hospital resources by strategy*

	CLI (n=)	DBS (n=)	Difference** CLI vs DBS
	Mean (95% BCa CI)	Mean (95% BCa CI)	Mean (95% BCa CI)
Screening for suitability			
preop. outpatient consultation			
inpatient stay			
on-/off-phase evaluation			
evaluation / nasogastric tube			
vitamin examinations			
other laboratory			
preop. anesthetic evaluation			
EKG			
MRI-brain	NA		
Continuous Levodopa Infusion			
CLI-pump			
CLI-cassettes			
PEG-jejunostomy placement			
tube replacement			
Deep Brain Stimulation			
(re)implantation			
electrode replacement			
extension cable replacement			
battery exchanges			

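### Worst-case scenario A and the ITT best case assign PDQ-39 extremes in the wrong direction: lowest is best health and highest is worst, so each rule tests the opposite of its label

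*SAP*

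**What the plan says.** The clinical part of the SAP defines the main outcome as "change from baseline to 12 months after initiation of treatment in PDQ-39 (score 0-100") and does not say which end of the scale is good. The health economics part does. Under *Health outcomes*, dimension scores run from "0 (perfect health as assessed by the measure) to 100 (worst health as assessed by the measure"), and change is month 12 minus baseline. Under *Incremental analysis*, willingness to pay is expressed "per additional unit decrease in change in PDQ-39". A higher score is therefore worse, and a negative change is improvement.

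Two sensitivity analyses of the main clinical outcome assign extreme scores.

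- *Patient replacement and missing data*, for patients with a missing 12-month score: "Possible worst-case scenarios were: (A) to assign the lowest assessed PDQ-39 in both treatment arms". The premise in the same paragraph is "Loss to follow-up because of clinical improvement was deemed unlikely". Scenario B is the alternative worst case, and the more applicable of the two is to be chosen.
- *Sensitivity analyses*, for patients who left the study immediately after randomisation. The reason given is that, for those "for whom the main clinical outcome at 12 months was missing, a favorable outcome was possible". The missing score is then "imputed with the highest PDQ-39 in the treatment arm the patient had been allocated to".

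**The concern.** A worst case should give lost patients poor health, and a best case good health. On this scale the two rules do the reverse.

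The SAP expects outcomes to be missing not at random, and these scenarios are part of how it tests that. The ITT sensitivity analyses are also its stated check on having moved the primary population from ITT to mITT after several patients refused CLI at once. If scenario A is selected, it carries over into the ITT worst case as well.

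Run as written, scenario A favours whichever arm has more missing scores. If that arm is also ahead, the reported worst case enlarges its lead and gives false reassurance. The best case penalises the arm that lost quitters when it was meant to credit it.

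**Working it through.** **Direction.** The labels and the scale, side by side:

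| Rule | Score assigned | Health on the 0 (best) to 100 (worst) scale | Stated reason |
|---|---|---|---|
| Worst case A | lowest | best observed | loss through improvement unlikely |
| ITT best case | highest | worst observed | favourable outcome possible |

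Reading lowest as lowest change does not help: change is month 12 minus baseline, so the lowest change is the largest improvement. Neither document defines a reversed scale.

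**Inputs for size.** Protocol section 4.4 gives 33 per arm, SD 15, and 12-month means of 32 (DBS) and 43.9 (CLI). Its figures reproduce: 26/(1 − 0.2) = 32.5, rounded up to 33; the difference detectable with 26 per group by t-test at 80% power is 11.89, against 11.9 stated. Missing counts are assumed. Scores are simulated as normal and clipped to 0–100, which lifts the DBS mean to 32.1 and makes the observed difference 11.8. Extremes are taken from 12-month scores, and baseline is assumed unrelated to missingness, so a shift in the 12-month mean equals the shift in mean change.

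**One case by hand, 7 missing per arm.** The expected lowest and highest of 26 observed scores are 4.3 and 61.7 (DBS), and 14.4 and 73.6 (CLI). New arm mean = observed mean + 7 × (extreme − observed mean)/33.

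- Lowest (as written): DBS 32.1 + 7 × (4.3 − 32.1)/33 = 26.2; CLI 43.9 + 7 × (14.4 − 43.9)/33 = 37.6. Both arms look healthier under a rule called worst case.
- Highest (as labelled): DBS 32.1 + 7 × (61.7 − 32.1)/33 = 38.4; CLI 43.9 + 7 × (73.6 − 43.9)/33 = 50.2.

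The arms move together, so the contrast hardly changes: about 11.4 against 11.8.

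**Unequal missingness, by simulation.** Gap in the CLI − DBS difference between A as written and A as labelled. Ranges cover equal means (32 in both arms) and means of 43.9 and 32:

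| Missing (CLI, DBS) | Extremes per arm | Extremes across both arms |
|---|---|---|
| 7, 7 | 0.0–0.4 | 0 |
| 8, 6 | 3.3–3.8 | 3.9–4.3 |
| 7, 4 | 5.1–5.5 | 5.9–6.5 |
| 7, 2 | 8.6–9.0 | 9.9–10.8 |
| 10, 3 | 11.6–12.1 | 13.6–15.0 |

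With few missing scores (equal means, extremes per arm) the gap is about 0.0 for 1 against 1 and about 1.8 for 3 against 2.

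**Which way it cuts** (means 43.9 and 32, extremes per arm, observed DBS advantage 11.8):

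- 4 CLI and 7 DBS missing: 11.8 + 2.2 = 14.0 as written; 11.8 − 2.6 = 9.2 as labelled.
- 7 CLI and 2 DBS missing: 11.8 − 4.5 = 7.3 as written; 11.8 + 4.4 = 16.2 as labelled.

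**ITT best case.** One quitter moves the arm mean by +0.9 (worse) where about −0.9 was meant; five move it by +4.6 where −4.3 to −4.5 was meant. The discrepancy is about 1.8 points per quitter (for one quitter at mean 32: 0.94 + 0.87 = 1.81).

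**The case against.** The intent can be recovered. The labels and reasons fix the direction, and scenario B, read literally, subtracts half of −1.6 and so adds 0.8 points, which is correctly worse. The authors probably meant lowest quality of life. The SAP and the health economics plan are one document, so the scale direction is stated somewhere in it.

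The reach is also narrow. A is one of two possible scenarios and may not be chosen. It is applied first in the mITT population, which excludes refusers, so the CLI refusals say little about imbalance there, and 33 per arm overstates that denominator. The best case touches only immediate quitters without a 12-month score, and ITT results go to supplements. Other analyses also address non-random missingness.

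Nor is the corrected rule always the harder test. With 7 CLI and 4 DBS missing, the written rule cuts the DBS advantage to 9.0 (p < 0.05 in 54% of simulated trials), while the corrected rule raises it to 14.4 (91%), against 11.8 (82%) in observed data.

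The limits on reach and the two-sided effect stand, and they keep this below a threat to the main result. The point about intent does not remove the error: syntax written from the words would take the minimum for A and the maximum for the best case. Two mirror-image slips suggest confusion over direction that could pass into the code unnoticed.

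**Conclusion.** The concern holds. Both rules are wrong as written on the document's own scale, and this needs no assumption about the data.

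The size does rest on assumptions: the protocol's planning values, near-normal scores and assumed missing counts. On these, scenario A is off by next to nothing when missingness is equal and extremes are taken per arm, by about 2 points for 3 against 2 missing, and by 5 to 12 points for the larger imbalances from 7 against 4 to 10 against 3. Taking extremes across both arms enlarges the larger figures.

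The primary mITT t-test, multiple imputation, conformity scenario, as-treated and per-protocol analyses, and the QALY and cost shifts are unaffected. It should be fixed, but it does not undermine the main analysis.

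Three nearby wordings are unclear rather than reversed, and the conclusion does not depend on them:

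- Scenario B refers to a scenario 1 that is never named, presumably the conformity scenario.
- Scenario A does not say plainly whether its extreme is taken within each arm or across both.
- The health economics shift "increasing actually imputed PDQ-39 summary index scores changes by 20% and 40"% depends on sign: an imputed change of −8 becomes −8 × 1.2 = −9.6 (better) if scaled, or −8 + 0.2 × 8 = −6.4 (worse) if a fifth of its size is added.

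**What to change.** - State with the main clinical outcome that a higher PDQ-39 is worse and a negative change is improvement.
- Worst case A: assign the highest observed 12-month PDQ-39, and say whether within each arm or across both.
- ITT best case: assign the lowest observed 12-month PDQ-39 in the allocated arm.
- Scenario B: write it as the conformity mean plus 0.8 points.
- Health economics PDQ-39 shift: add 20% or 40% of the absolute imputed change, so that every shift is towards worse health, as that section intends.

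The cost is two swapped words, four short clarifications and the matching lines of syntax. No new data are needed. It should be done before database lock: the direction of an extreme-value imputation corrected after results are seen would look data-driven.

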4.4 Sample size calculation

RCT

The primary objective of the study is to realize an efficient allocation of resources to the available treatment options in advanced PD. For this, primarily an economic evaluation will be carried out and the sample size has been calculated accordingly. Society's willingness-to-pay (WTP) per Quality Adjusted Life Year (QALY) may be indicative of whether or not CLI is affordable compared to DBS. The Dutch Raad voor de Volksgezondheid (RvZ) reported a value of €80,000 per additional QALY in 2006 as a potential upper limit of affordability. Explicitly, the figure is reported by the RvZ as a potential, but also unofficial limit: it should

Version 7: 23-10-2019 16 of 48

not be taken as a definite one. Other arguments based on patient preference or access to health care should be taken into account as well. Considering that CLI may be a less invasive intervention and access to health care is easier to facilitate when two interventions can be provided, a more lenient upper limit for the extra societal costs per additional QALY may be appropriate here. We propose a sample size calculation based on a WTP per additional QALY of €120,000 (50% above the RvZ figure). Based on the net health benefit formula suggesting that differences in QALYs between the interventions should be larger than the difference in costs (i.e., €34,174 a year) divided by the maximum WTP (i.e., €120,000 per QALY) in order for one intervention to be accepted as more efficient than another intervention, CLI treatment should at least outperform DBS treatment by 0.2847 QALY per year. Based on literature data with comparable costs estimates, [6] we anticipate standard deviations (SD) for QALYs up to 0.35 and for total costs up to €10,000 (factoring in a 12-month follow-up and non-responders).

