To achieve 80% power and given a two-sided significance level of 0.05, up to 26 patients per group (or 52 in total) are needed to detect a difference of at least 0.2847 QALY for WTP-values up to €120,000 and a worst case scenario of zero correlation between costs and clinical effect, using a two-group t-test. Accounting for a possible dropout of 20%, we will randomize 66 patients (33 per group). With this sample size and given the same test conditions (power, type-I error rate, test chosen, drop-out rate) we are also able to detect a difference in mean PDQ-39 scores between both groups of 11.9, assuming an expected mean score of 32 in the DBS group and a standard deviation of 15.

Motivation for standard deviations for QALY

Literature data [8-10] show that the standard deviation for PDQ-39 scores from operated PD patients equals 15 points and that a 4 to 5 points difference is associated with a QALY difference of approximately 0.1,[16] suggesting a standard deviation for QALYs of up to 0.35.

Patient preference trial

We (conservatively) estimate that during the inclusion period a total of 180 patients (60% of the eligible patients) may decline to participate in the RCT, but are willing to take part in the preference observational study. Based on our clinical experience it is expected that 60% of these patients (n=108) prefers DBS, against 40% (n=72) preferring CLI.

When comparing the effect of DBS treatment of patients who express a preference for that treatment with the effect of DBS treatment in the randomised patients, and given the same test conditions (power, type-I error rate, two group t-test) we are able to detect a difference in

Version 7: 23-10-2019 17 of 48

mean PDQ-39 scores between both groups of 8,4, assuming an expected mean score of 32 in the randomized DBS group and a standard deviation of 15.

In case only 120 patients (40% of the eligible patients) agree to take part in the preference observational study, we are able to detect a difference in mean PDQ-39 scores between both DBS groups of 8,9.

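### The predefined worst cases barely test informative dropout on the PDQ-39: scenario B adds 0.8 points per lost patient, scenario A as written takes the best score, and no rule decides between them

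*SAP*

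**What the plan says.** Under the synopsis of protocol development, the SAP notes that comorbidity reduced the completeness of follow-up and that the data may over-represent healthier patients. Under 'Patient replacement and missing data', main clinical outcome, the plan is as follows:

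- **Primary handling.** The 9-month value, adjusted by the arm's mean change, is used where available (approach I). Otherwise there is multiple imputation by predictive mean matching within each arm, using baseline variables, earlier outcomes and adverse events (approach II).
- **Sensitivity handling.** Because values are expected to be missing not at random, a conformity scenario gives a lost patient the mean PDQ-39 of the allocated arm. Worst case A gives the lowest PDQ-39 observed. The other worst case is "B) scenario 1 minus ½ minimal clinically important difference", with that difference taken as −1.6.
- **Choice.** Treating physicians report death, treatment in use, residence and modified Rankin score for lost patients. On that basis, "the most applicable worst-case scenario was selected and justified".

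The SAP section on sensitivity analyses then applies to the ITT population the conformity scenario and "the most applicable worst case scenario chosen for the mITT analysis". It adds a best case for patients who quit immediately after randomization, using the highest PDQ-39 in their arm. The HEAP, under 'Health outcomes', codes the PDQ-39 dimensions from 0 (perfect health) to 100 (worst).

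**The concern.** If sicker patients are the ones lost, an analysis that treats them as average for their arm flatters the arm that loses more. A worst case should show how much worse the lost patients would have to be before the conclusion changes.

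If B is selected, the worst cases for both the mITT and the ITT population will sit almost on top of the conformity result. A report could then claim robustness to informative loss on a check that adds very little. If A is selected and applied as written, lost patients receive the best score seen. The choice also matters because A and B differ greatly in size and point in opposite directions, yet nothing fixes it in advance.

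**Working it through.** **Inputs from the documents**

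- Protocol 4.4: "CLI treatment should at least outperform DBS treatment by 0.2847 QALY per year"; "we anticipate standard deviations (SD) for QALYs up to 0.35 and for total costs up to €10,000"; willingness to pay €120,000; "To achieve 80% power and given a two-sided significance level of 0.05, up to 26 patients per group (or 52 in total) are needed"; 20% dropout; 33 randomized per group; PDQ-39 SD 15 and DBS mean 32; "we are also able to detect a difference in mean PDQ-39 scores between both groups of 11.9"; CLI mean 43.9.
- SAP: minimal clinically important difference −1.6.

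**Assumptions**

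- The starting point of B is the conformity scenario.
- The SD of the change score is 15. The protocol gives 15 for scores, and no SD for change is stated.
- There are 33 patients per arm in the analysis.

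**1. The plan's own figures reproduce.**

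- SD of net health benefit at zero correlation = √(0.35² + (10,000/120,000)²) = 0.3598.
- n = 2 × (1.960 + 0.842)² × 0.3598² / 0.2847² = 25.07, so 26 per group.
- 26/0.8 = 32.5, so 33 per group and 66 in total.
- With 26 per group and SD 15, the difference detectable at 80% power (noncentral t) is 11.89, against 11.9 stated.

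**2. Size of B.** Half of −1.6 is −0.8. Subtracting it adds 0.8 points, which is adverse on this scale. 0.8/15 = 0.053 SD.

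**3. Effect of B on the group difference, relative to conformity** = 0.8 × (share lost in one arm − share lost in the other). The standard error is 15 × √(2/33) = 3.69, and the CI half-width is 1.998 × 3.69 = 7.38.

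| Loss | Shift | Shift / SE | Shift as % of 11.9 |
|---|---|---|---|
| Equal in both arms | 0 | 0 | 0 |
| 3 of 33, one arm only | 0.07 | 0.020 | 0.6 |
| 7 of 33, one arm only | 0.17 | 0.046 | 1.4 |
| 13 of 33, one arm only | 0.32 | 0.085 | 2.6 |

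With 7 lost in one arm, 0.17/7.38 = 2.3% of the half-width.

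**4. Sensitivity to the assumed SD and n.**

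- If the score SD is 15 at both visits, the change SD is 15 × √(2(1 − ρ)). For ρ = 0.3, 0.5 and 0.7 the half-widths are 8.73, 7.38 and 5.71, and 0.17 is 1.9%, 2.3% and 3.0% of them.
- With 26 per arm, the half-width is 8.36 and the shift is 0.8 × 7/26 = 0.22, or 2.6%.

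**5. Which results could flip.** At an unchanged SE, only a two-sided p between 0.045 and 0.05 (7 lost in one arm) or between 0.041 and 0.05 (13 lost) could lose significance.

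**6. Shift that would be needed.** Per lost patient, with 7 lost in one arm, it is (observed difference − 7.38) × 33/7:

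- difference 8: 2.9 points;
- difference 10: 12.4 points;
- difference 11.9: 21.3 points.

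These are about 4, 15 and 27 times 0.8.

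**7. Simulation** (20,000 trials per setting, 33 per arm, SD 15, baseline-to-12-month correlation 0.3 to 0.7, assumed). With 7 lost per arm, B overturned 0.04% to 0.6% of results that were significant under conformity. The estimate does not move there, but the SE changes slightly. With 7 or 13 lost in one arm only, B overturned 0.4% to 8%.

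**8. Direction of A.** With normal scores truncated to 0–100, SD 15 and 26 observed per arm, the expected lowest score is about 4 (DBS) or 14 (CLI), and the highest about 62 or 74. A therefore places a lost patient about 32 − 4 = 28 or 44 − 14 = 30 points better than the arm mean.

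**The case against.** The strongest reply is that the scenarios were written down before database lock and without sight of patient data, that selection rests on clinical information about lost patients, and that other analyses also bear on missing data. Parts of this stand, and they limit what can be said.

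- **A reader might infer that no result could fail B.** That goes too far. With unbalanced loss, a borderline p-value can flip. Assigning one mean value can itself change a result relative to complete cases: about 1% to 4% of significant results at a true difference of 11.9, and 7% to 13% at 8, in the simulation. That comes mainly from the mean imputation, not from the 0.8 points. If the arm-mean change plus 0.8 is assigned instead, none flips, because constant values shrink the SE by about 22% with 7 of 33 lost per arm.
- **A reader might infer that the choice is made once outcomes are known.** The SAP ties it only to the physicians' reports. It neither states nor excludes knowledge of PDQ-39 results, and it does not say who chooses.
- **A reader might infer that only one worst case is reported.** This follows naturally from the word 'selected', but it is not stated.
- **A reader might infer that B is kinder than approach II.** It would be if lost patients started worse. The documents give neither a baseline gap nor a correlation, so no size can be attached.
- **A reader might infer that informative loss is never tested.** Other checks exist, but they do not fill this gap for the clinical outcome. Imputation on the total mITT population still assumes missingness at random. The as-treated analysis does not impute. A missed 12-month visit is a protocol violation, so those patients leave the per-protocol set. The HEAP shifts imputed PDQ-39 changes by 20% and 40%, but for the economic evaluation, and enlarging a negative change makes it more favourable. The ITT best case is in fact adverse on the stated scale, but it covers only patients who quit at once.

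A might also be meant as the lowest quality of life, not the lowest score. The text does not say so, and the ITT best case uses the highest score, so the direction needs to be stated.

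**Conclusion.** The point holds in this form. Against an expectation of data missing not at random, B moves the group difference by 0 with equal loss and by 0.17 points with 7 of 33 lost in one arm, about 2% to 3% of the CI half-width over the SDs and arm sizes considered. A, read literally, is not a worst case. The rule for choosing between them is absent, and the choice carries into the ITT analysis.

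The figures rest on reading the undefined starting point of B as the conformity scenario, on an SD of about 15 for change, and on 26 to 33 patients per arm. No plausible SD makes 0.17 points a serious test. The primary estimate is not affected. What is at stake is any claim that it is robust to informative loss.

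**What to change.** 1. Define the starting scenario that B refers to.
2. Correct A to the highest (worst) observed PDQ-39, say whether this is taken within arm or across arms, and correct the direction of the ITT best case to match.
3. Replace B by a prespecified range of adverse shifts added to the approach II imputations, so that imputation variance is kept. Shifts of 5, 10 and 15 points, up to the planning SD, are one example. With 7 of 33 lost in one arm they move the difference by 1.06, 2.12 and 3.18 points (shift × 7/33), or 14%, 29% and 43% of 7.38. Apply them in each arm alone and in both, and continue to the tipping point where the conclusion changes.
4. Delete the selection step and report all scenarios for both mITT and ITT. Use the physicians' reports only to comment on which shifts are plausible.

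The cost is SAP wording and one supplementary table. The downside is that the results may look less robust.
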